## 4 STUDY DESIGN

### 4.1 OVERALL DESIGN

The study is a single site double-blind, placebo-controlled, phase 1b randomized trial to evaluate the safety and preliminary pharmacologic activity of GSK2256294 in patients with

aneurysmal SAH. We hypothesize that inhibition of the sEH enzyme will be safe in patients with SAH, and result in increased EETs availability at the neuroendothelium, eventually leading to reduced neuroinflammation. Up to 30 patients will be equally randomized to receive once daily enteral administration of either 10 mg dose of GSK2256294 or placebo for a duration of 10 days.

## 4.2 SCIENTIFIC RATIONALE FOR STUDY DESIGN

This is a safety and proof of concept study. A randomized trial is needed to determine the effect of GSK2256294 on EETs metabolism, because EETs levels vary over the natural course of recover after SAH, and a placebo group is needed for comparison. Randomization and double blinding additionally limit the influence of potential confounders and selection bias.

## 4.3 JUSTIFICATION FOR DOSE

GSK2256294 exposures are approximately dose proportional over the range of 6 mg to 20 mg. High levels of enzyme inhibition was observed with single doses of 6 to 20 mg, and sustained at greater than 95% for 24 hours at a dose of 10 mg in repeat dosing trials. A 10-day administration schedule was chosen because this represents the highest risk time period for development of neuroinflammatory changes related to delayed cerebral ischemia.

## 4.4 END OF STUDY DEFINITION

A participant is considered to have completed the study if he or she has completed all phases of the study including the last visit shown in the SoA, Section 11.

The end of the study is defined as completion of the last visit or procedure shown in the SoA in the trial globally.

# 5 STUDY POPULATION

## 5.1 INCLUSION CRITERIA

In order to be eligible to participate in this study, an individual must meet all of the following criteria:

- Age  $\geq$  18
- Head CT evidence of subarachnoid hemorrhageDigital subtraction cerebral angiography or CT angiogram documenting the presence of a cerebral aneurysm.

## 5.2 EXCLUSION CRITERIA

An individual who meets any of the following criteria will be excluded from participation in this study:

- Symptom onset compatible with SAH of > 3 days prior to admission to OHSU

Evidence of QTc prolongation > 500ms on admission  
Baseline AST and ALT > 2x normal reference range  
Administration of any of the following inducers/inhibitors of CYP3A4: ritonavir, indinavir, nelfinavir, saquinavir, clarithromycin, telithromycin, chloramphenicol, ketoconazole, itraconazole, nefazodone, cobicistat or enzalutamide.  
Current pregnancy, based on urine HCG positive pregnancy test  
Preexisting severe neurologic deficit or condition  
Chronic renal failure requiring dialysis  
Severe terminal disease with life expectancy <6 months  
Unable to read or understand written or spoken English or Spanish  
Refusal of informed consent

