a cerebral aneurysm. An individual who meets any of the following criteria will be excluded from participation in this study: evidence of prolonged QTc >500 milliseconds, baseline AST and ALT > 2x normal reference values, administration of strong inducers/inhibitors of CYP3A4, symptom onset compatible with SAH of  $\geq 3$  days prior to admission to Oregon Health and Science University Neurosciences Intensive Care Unit (OHSU NSICU), unable to speak or understand English or Spanish, current pregnancy based on urine HCG positive pregnancy test, preexisting severe neurologic deficit or condition, chronic renal failure requiring dialysis, severe terminal disease with life expectancy <6 months, or refusal of informed consent.

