## 3 OBJECTIVES AND ENDPOINTS

- **Primary Objective:** Determine the safety of administration of GSK2256294 in patients with aneurysmal SAH.

Frequencies of AEs and SAEs: We will compare AEs and SAEs between the drug and placebo groups. We will also compare daily safety labs (serum sodium, blood glucose, blood urea nitrogen (BUN), creatinine, hematocrit, peripheral white blood cell count) between the groups. Specific to this patient population, we will also specifically screen for disease related events including seizure, new onset cardiomyopathy, NSTEMI/STEMI, hyponatremia, hospital acquired infection, mechanical ventilation, and thromboembolic events. We will describe the severity of headache (on a daily scale of 0-10).

**Justification:** Prior phase 1 studies of GSK2256294 have been in healthy volunteers with limited physiologic monitoring. The most common adverse event was headache. We will assess safety in this critically ill patient population with special focus on common sequelae of subarachnoid hemorrhage.

- **Secondary Objective:** Determine the pharmacodynamic effects of administration of GSK2256294 in patients with aneurysmal SAH.

To evaluate the effect of enzymatic inhibition on circulating EETs levels, we will measure day 7 and day 10 serum EET/DHET ratios. EETs levels will be measured using liquid chromatography and mass spectroscopy.

To evaluate the possible effect of enzymatic inhibition on CSF EETs levels we will measure day 7 and day 10 CSF EET/DHET ratios, and compare the drug and placebo groups. We will also measure other lipid metabolic substrates of sEH at days 7 and day 10, specifically serum epoxyoctadecenoic acid (EPOME) and dihydroxyoctadec-12-enoic acid (DPOME), to assess sEH enzyme activity.

To evaluate more downstream effects on measures of endothelial injury and neuroinflammation, we will measure multiple biomarkers in the blood and CSF at day 7 and day 10 (Table 1). The biomarkers chosen are surrogate endpoints representing pathways of the inflammatory cascade associated with clinical endpoints in SAH.

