### 8.3 STUDY DRUG ADMINISTRATION SCHEDULE

The investigational pharmacy will maintain blinding, labeling and dispensing to healthcare providers of the study drug as described above. The first dose of study drug will be administered immediately after randomization. Subsequent doses will be administered daily in the morning for a total of 10 days. The preferred route of administration is orally, but patients with SAH are often neurologically compromised and unable to safely swallow. A suspended formulation will be administered via the orogastric or nasogastric route for patients deemed unsafe to swallow.

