### 8.4 SAFETY ASSESSMENTS

#### 8.4.1 DAILY ASSESSMENTS

Daily assessments will be performed beginning on the randomization day (day=1), and on subsequent study days that subjects receive study drug (days 2-10). The randomization day will be defined as the time from randomization to the next 6:59 AM. All subsequent study days will be defined as a 24-hour window between 7:00AM and 6:59 AM the following day. Study staff will perform daily assessments from data collected from the medical record as part of patients' routine intensive care unit treatment and monitoring, or by patient interview. These include:

- **Vital Signs:** every four hour vital signs including blood pressure from noninvasive and arterial sources, heart rate, body temperature, and the presence of absence of mechanical ventilation;
- **Cardiac Monitoring:** daily QTc interval, and the presence of cardiac arrhythmias on continuous EKG monitoring.
- **Intake and Output:** total fluids administered and total drain and urine output;
- **Laboratory Assessments:** serum sodium, blood glucose, BUN, creatinine, hematocrit, peripheral white blood cell count;
- **Neurologic Assessments:** GCS, MCA transcranial Doppler velocities and Lindegaard ratios, and headache severity;
- **Concomitant medications:** Daily administration of selected classes of hospital administered concomitant medications will be reviewed for all study subjects during the first 10 days.

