#### 8.4.2 DISEASE RELATED AND ADVERSE EVENT TRACKING

Daily disease related event log and adverse event log forms will be completed. Specific complications common in patients with SAH will be abstracted from the medical record with the date and time of onset and resolution. These include:

- **Seizure:** Electrographic or generalized tonic clonic seizure activity;
- **Cerebral angiography** results and interventions, including the distribution and severity of cerebral vasospasm;
- **Neurologic deteriorations attributable to DCI:** Defined as the development of new focal neurological signs or decreased level of consciousness that resulted in a decrease in the Glasgow Coma Scale (GCS) score of 2 points, lasting at least 1 hour, and not attributable to infection, changes in sedation, or non-ischemic cerebral pathology such as acute hydrocephalus);
- **The need for intervention to manage DCI:** Defined as use of augmented blood pressure goals, cardiac index monitoring, or intra-arterial vasodilator therapy;
- **New onset or previously undocumented myocardial dysfunction:** left ventricular ejection fraction (LVEF)  $\leq$  45%, or a  $>$  10% change from baseline LVEF, LV contractile pattern consistent with neurogenic cardiomyopathy at any measured LVEF, or new wall motion abnormalities;
- **NSTEMI/STEMI:** ST segment changes on 12 lead ECG suspicious for myocardial ischemia, or any elevation of serum troponin above reference range;
- **Hospital acquired infection:** Culture data resulting in the use of antibiotics for  $>$  72 hours;
- **Liver dysfunction:** Liver function tests will be assessed on study day 7. AST or ALT  $>$  3x above baseline values will be identified as an adverse event
- **Thromboembolic events:** Imaging-documented presence of extracranial venous or arterial thrombus.

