#### 9.4.3 ANALYSIS OF THE PRIMARY ENDPOINT

Safety will be assessed by clinical review of all relevant parameters including vital signs, laboratory values, adverse events, serious adverse events, disease related events, and mortality. Unless specified otherwise, the safety analyses will be conducted for the safety population.

Summary tables and listings will be provided for all reported adverse events, defined as adverse events that start on or after the first administration of study drug. The reported adverse event term will be assigned a standardized preferred term.

Adverse events will be summarized based on the number and percentage of patients experiencing the event. In the event a patient experiences repeat episodes of the same adverse event, then the event with the highest severity grade and strongest causal relationship to study treatment will be used for purposes of incidence tabulations. Tabular summaries will be provided for all adverse events, the relationship to study drug treatment the maximum severity grade, action taken, and whether the event qualified as SAE or not.

Daily safety laboratory test results will be summarized in a descriptive manner by calculating the mean, standard deviation, median, and range. Directional shifts (comparing baseline grade with worst post-baseline grade) will be analyzed using standard shift tables. The shift table will present directional shifts from baseline to above or below the laboratory standard normal range using the maximum increase and/or decrease observed throughout the course of treatment/observation.

Vital signs will be summarized in a descriptive manner by calculating the mean, standard deviation, median, and range in the same manner described for laboratory values.

All deaths will be reported in a patient listing, which will include the primary cause of death and the number of days between the date of the last dose of study drug and death.

---

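### The liver exclusion requires AST and ALT both to exceed twice normal, so one enzyme raised to any level does not by itself exclude a patient

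*Combined protocol and SAP*

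**What the plan says.** **Entry.** Section 5.2 lists as an exclusion "Baseline AST and ALT > 2x normal reference range". The synopsis (section 1.1) gives the same rule as "baseline AST and ALT > 2x normal reference values". No other listed exclusion covers a single raised liver enzyme. Section 8.1 provides for baseline liver tests to be sent if routine care has not already produced them, and section 6.3 makes confirmation of eligibility part of the randomization procedure.

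**On treatment.** Section 8.4.2 reads "Liver function tests will be assessed on study day 7. AST or ALT" and goes on to define a rise to more than three times the baseline value as an adverse event. The same two enzymes are therefore joined by *or* here, and the yardstick is the patient's own baseline, not the reference range.

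**Timing.** The first dose follows randomization on day 1, and section 8.3 states "Subsequent doses will be administered daily in the morning for a total of 10 days". The daily laboratory panel in section 8.4.1 is "serum sodium, blood glucose, BUN, creatinine, hematocrit, peripheral white blood cell count", with no AST or ALT. Research blood is drawn at baseline, day 7 and day 10 (section 8.5.1). Section 11, the Schedule of Activities, refers to an attachment that was not supplied.

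**The concern.** An exclusion on liver enzymes normally serves to keep out patients with existing liver injury. Joined by *and*, it does so only when both enzymes are raised. One enzyme can be at any level, with no cap, provided the other stays at or below 2x. Staff who confirm eligibility line by line would be right to pass such a patient.

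The entry rule also feeds the on-treatment rule. Because the adverse event is defined relative to baseline, a patient who enters with one high enzyme needs a very large further rise before that enzyme triggers the definition.

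Safety is the primary objective (section 3). Section 2.3.2 says that this is the drug's first use in a critically ill population, section 2.3.1 says that the safety database is limited, and section 2.2 says that elimination is mainly by biliary secretion and metabolism. The liver check should therefore work as it appears to be meant to. A secondary question is whether one on-drug liver test is enough for a ten-day course.

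**Working it through.** The plan gives no figure to reproduce. The check is one of logic and counting.

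**1. The two entry rules on example values.** Enzymes are in multiples of the upper reference limit. The values are illustrative; the documents give no frequency for discordant enzymes.

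- Rule as written: exclude if AST > 2 and ALT > 2.
- Alternative: exclude if AST > 2 or ALT > 2.
- On-treatment flag for each enzyme (section 8.4.2, taking the rule as three times baseline): 3 × baseline.

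| AST | ALT | Excluded, *and* | Excluded, *or* | AST flagged above | ALT flagged above |
|---|---|---|---|---|---|
| 1 | 1 | no | no | 3 | 3 |
| 2.1 | 1 | no | yes | 6.3 | 3 |
| 10 | 1.9 | no | yes | 30 | 5.7 |
| 1.9 | 10 | no | yes | 5.7 | 30 |
| 2.1 | 2.1 | yes | yes | 6.3 | 6.3 |

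The rules differ exactly when one enzyme is above 2x and the other is not.

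**2. Effect on the flag.** Under *or*, every enrolled patient has both enzymes at or below 2x, so the flag is at most 3 × 2 = 6x the upper reference limit. Under *and*, only the lower of the two enzymes is bounded by 2x. The other has no bound, and neither does its flag.

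**3. Timing, from the supplied text only.** With one dose on each of days 1 to 10 and none missed:

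- Day 7 test drawn after that day's dose: 10 − 7 = 3 doses follow it.
- Day 7 test drawn before that day's dose: 10 − 6 = 4 doses follow it.
- Day 10 test: 10 − 10 = 0 doses follow it if drawn after the dose, 10 − 9 = 1 if drawn before.

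**4. Exposure at day 7.** Section 2.2 gives a half-life of 20 to 30 hours and steady state within 6 to 8 days. Assuming simple first-order accumulation and 24-hour spacing, dose 7 comes 6 × 24 = 144 hours after dose 1.

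- Half-life 30 hours: 144/30 = 4.8 half-lives, and 1 − 2^(−4.8) ≈ 96% of steady state.
- Half-life 20 hours: 144/20 = 7.2 half-lives, and 1 − 2^(−7.2) ≈ 99%.

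The day 7 test therefore samples close to plateau exposure. The later doses add duration, not much level.

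**The case against.** **The conjunction is probably loose drafting.** It can be read as a limit applied to each enzyme in turn, and other wording in the document is loose too: the symptom-onset limit is 3 days or more in the synopsis but more than 3 days in section 5.2. The *or* in section 8.4.2 serves a different purpose and does not prove what the entry rule intended. All this is fair. It does not remove the problem, because the literal wording appears twice and nothing supplied corrects it. A reader might infer that patients with markedly abnormal enzymes will be enrolled. The documents support only that they are eligible.

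**Other safeguards exist.** Section 8.6.4 has deterioration of a baseline condition recorded as an adverse event, and section 7.2 lets an investigator withdraw a participant for a laboratory abnormality. Both stand, though a rise without symptoms still needs a test to be seen.

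**The timing point rests partly on an unseen attachment.** A reader might infer from the 3 or 4 later doses that 30% to 40% of treatment goes unmonitored for the liver. That is too strong. The Schedule of Activities may list a later test, day 7 is already near steady state, and section 2.2 describes earlier once-daily dosing for 14 days at 6 mg and 18 mg, longer than this trial and up to a higher dose than its 10 mg. Those subjects were not critically ill, so a later test keeps some value, but only as a conditional addition.

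**Analysis.** A reader might also infer that AST and ALT escape the safety analysis, because the shift tables in section 9.4.3 are introduced by "Daily safety laboratory test results will be summarized in a descriptive manner" and neither enzyme is in the daily panel. That does not follow. The same section calls for clinical review of laboratory values, and a rise that meets the section 8.4.2 definition enters the adverse event tables.

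**Conclusion.** The entry-rule point holds. As written in sections 1.1 and 5.2, a patient with one enzyme above 2x, without limit, is eligible if the other is at or below 2x. Through the baseline-relative rule in section 8.4.2, that patient's on-treatment flag for the raised enzyme also has no ceiling, against at most 6x the upper reference limit under *or*. This rests on a literal reading of the wording. How many patients it would affect cannot be said from the documents.

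The timing point is secondary and conditional. The supplied text schedules one on-drug liver test, near steady state, in a ten-day course. Whether that is the whole schedule cannot be settled without the attachment.

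A reader might take either point as a sign of liver toxicity. The documents do not support that: section 2.3.1 describes no human liver signal, and the rat liver changes in section 2.2 were at 1000 mg/kg/day. The point is a tightening of the safety check in a trial whose primary objective is safety.

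**What to change.** In sections 1.1 and 5.2, change the exclusion to AST **or** ALT more than 2x the upper limit of the reference range. This is one conjunction and a clearer reference point in two places. It needs no new screening test, since baseline liver tests are already obtained. The downside is possibly a few more screen failures.

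Then check the Schedule of Activities. If it lists a liver test after day 7, no change is needed. If it does not, add a clinical AST and ALT at the existing day 10 blood draw, preferably after that day's dose. Send it as a routine clinical sample, because the study plasma is frozen for batch assay (sections 8.5.2 and 8.5.3). The cost is one assay per patient, 1 × 30 = up to 30 in all, and a little extra blood. If the sample has to precede the day 10 dose, one of the ten doses still has no test after it.

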### 5.3 SCREEN FAILURES

Screen failures are defined as participants who are eligible to participate based on inclusion criteria, but meet any of the exclusion criteria. A minimal set of screen failure information is required to ensure transparent reporting of screen failure participants, to meet the Consolidated Standards of Reporting Trials (CONSORT) publishing requirements and to respond to queries from regulatory authorities. Minimal information includes screen failure details, eligibility criteria and reason for patient exclusion.

### 5.4 STRATEGIES FOR RECRUITMENT AND RETENTION

The study population will draw from all adult patients admitted to the OHSU NSICU, part of a comprehensive stroke center certified by the American Heart Association and Joint Commission for Accreditation of Healthcare Organizations, with a catchment area including the state of Oregon, Southwest Washington and Northern California. Approximately 80-100 patients with aneurysmal SAH are admitted each year. All patients admitted with SAH have cerebral angiography or CT angiogram early after admission. Research personnel will review patients from the ICU census for eligibility on a daily basis.

To ensure completeness of follow up procedures, we will collect contact information from the patient, the patients legally authorized representative (LAR), the primary care provider (PCP), and the disposition location (facility) contact information at hospital discharge. The CareEverywhere electronic medical record network and obituary screening will be used to identify deaths.

## 6 STUDY INTERVENTION

### 6.1 STUDY INTERVENTION(S) ADMINISTRATION

#### 6.1.1 STUDY INTERVENTION DESCRIPTION

GSK2256294, a potent and selective inhibitor of soluble epoxide hydrolase, will be administered to the treatment group, and a matched placebo will be administered to the placebo group for a total treatment course of 10 days.

---

## 6.1.2 DOSING AND ADMINISTRATION

Subjects will receive either 10mg of GSK256294 or matched placebo. The first dose of drug or placebo will be administered after informed consent, randomization and collection of baseline laboratory samples. Subsequent doses will be administered daily for a total treatment course of 10 days. Subjects who are able to swallow will receive the capsule formulation orally. Subjects not able to swallow will receive the contents of the capsule suspended in normal saline, administered via orogastric or nasogastric enteral access by the bedside nurse. Missed doses will be administered as soon as feasible. No restriction to food intake is necessary.

## 6.2 PREPARATION/HANDLING/STORAGE/ACCOUNTABILITY

---

### 6.2.1 ACQUISITION AND ACCOUNTABILITY

GlaxoSmithKline will supply the drug capsule and matched placebo to the OHSU investigational pharmacy. At the end of the trial, unused product will be returned to GlaxoSmithKline or destroyed.

---

### 6.2.2 FORMULATION, APPEARANCE, PACKAGING, AND LABELING

GSK2256294 is available in capsule form. The capsules are opaque Swedish orange hard gelatin, containing a white powder. Matched placebo capsules which are also opaque Swedish orange containing white powder will be administered to the placebo group. The capsules are packaged into white, opaque, high density polyethylene bottles with child-resistant closures. The label for the clinician administering the drug will identify the medication as the "Study Drug". The label will contain the study number, subject number, quantity of product, and directions for use.

---

### 6.2.3 PRODUCT STORAGE AND STABILITY

The capsule will be stored at room temperature, and the drug is stable up to 30°C.

---

### 6.2.4 PREPARATION

Capsule packaging will be labeled as described above and dispensed from the OHSU investigational pharmacy to the OHSU NSICU on a daily basis. At the time of administration, the bedside nurse will administer the capsule formulation orally in patients able to swallow. If patients are unable to swallow, the bedside nurse will open the capsule and suspend the contents in 10mL of 0.9% normal saline, and administered immediately after suspension via orogastric or nasogastric tube.

